4.1.4 Imputation rules

Missing safety data will generally not be imputed. However, safety assessment values of the form of “< x” (i.e., below the lower limit of quantification) or > x (i.e., above the upper limit of quantification) will be imputed as “x” in the calculation of summary statistics but displayed as “< x” or “> x” in the listings. Additionally, AEs that have missing causality (after data querying) will be assumed to be related to study drug. Missing CTCAE grades will not be imputed.

Patients with a partial date of birth (i.e. for those countries where year of birth only is given) will have an assumed date of birth of 1st Jan [given year]) for calculation of age at informed consent.

Partial dates for the following modules will be imputed: prior cancer therapy, previous radiotherapy and prior and concomitant medications and adverse events, as well as for other modules, where required.

The original incomplete or missing dates will be presented in the listings.

Adverse events and medications

Adverse events: all AEs will be considered as treatment-emergent unless the opposite can be clearly stated. Imputation will be done only in the context of identifying TEAEs.

Medications/therapies: all medications will be considered as concomitant unless the opposite can be clearly stated.

In practice, for adverse events and medications, original incomplete or missing start dates will be imputed as below:

- Missing day: impute the 1st of the month unless month and year are the same as month and year of first dose of study drug then impute first dose date;
- Missing day and month: impute 1st January unless year is the same as first dose date then impute first dose date;
- Completely missing: impute first dose date unless the end date suggests it could have started prior to this in which case impute the 1st January of the same year as the end date.

When imputing a start date, ensure that the new imputed date is sensible, i.e., is prior to the end date of the AE or medication.

Original incomplete or missing stop dates for adverse events and medications/therapies will be imputed as below:

- Missing day: impute the last day of the month;
- Missing day and month: impute 31st December. Flags will be retained in the database indicating where any programmatic imputation has been applied, and in such cases, any durations would not be calculated.

If a patient is known to have died where only a partial death date is available then the date of death will be imputed as the latest of the last date known to be alive +1 from the database and the death date using the available information provided:-

- a. For Missing day only – using the 1st of the month
- b. For Missing day and Month – using the 1st of January

Duration of AE will not be derived using imputed dates.

4.2 Analysis methods

Efficacy data will be summarised and analysed using the mITT set, and selected analyses repeated on the ITT set.

[Table 9](#) below details which endpoints are to be subjected to formal statistical analysis, together with pre-planned sensitivity analyses, making it clear which analysis is regarded as primary for that endpoint.

Table 9 Study endpoints

Endpoints analysed	Notes
Progression-free survival	
Stratified log-rank tests for:
 
 
• Primary analysis using BICR tumour RECIST 1.1 assessments 
• Sensitivity analyses using BICR tumour RECIST 1.1 data 
 
• Interval censored analysis – evaluation time bias 
• Analysis using alternative censoring rules – attrition bias 
• Analysis by excluding sCRT patients with 1 concurrent chemotherapy and radiation cycle 
• Analysis accounting for COVID-19 deaths 
• Sensitivity analysis using study site Investigator tumour RECIST 1.1 data – ascertainment bias 
Analysis in the presence of non-proportional hazards assumption – Stratified Max-combo test
 
Additional analysis using Cox proportional hazards models to determine the effect of covariates on the HR estimate
 
Additional analysis using Cox proportional hazards model to determine the consistency of treatment effect between stratification factors via the approach of Gail and Simon 1985.
 
Subgroup analysis using Cox proportional hazards model

Overall survival	
Stratified log-rank test for:
 
 
• Secondary analysis 
• Sensitivity analysis using alternative censoring rules – attrition bias 
• Analysis accounting for COVID-19 deaths 
Analysis in the presence of non-proportional hazards assumption – Stratified Max-combo test
 
Additional analysis using Cox proportional hazards models to determine the effect of covariates on the HR estimate
 
Subgroup analysis using Cox proportional hazards model

Additional analysis using Cox proportional hazards model to determine the consistency of treatment effect between stratification factors via the approach of [Gail and Simon 1985](#).

Proportion of patients alive at 12 and 24 months from randomisation	KM estimates of survival at 12 and 24 months
Objective response rate	Logistic regression for: 
 • Secondary analysis using BICR tumour RECIST 1.1 data • Sensitivity analysis using study site Investigator tumour RECIST 1.1 data
Duration of response	KM estimates for DoR using BICR tumour data
Progression-free survival at 12 and 18 months from randomisation	KM estimates of progression-free survival at 12 and 18 months
Time from randomisation to second progression ^a	Stratified log-rank test
Time to death or distant metastasis	Stratified log-rank test using site BICR tumour RECIST 1.1 data
Time to first subsequent therapy or death	Stratified log-rank test
Time to second subsequent therapy or death	Stratified log-rank test
Symptom improvement rate (EORTC QLQ-C30 and QLQ-LC13 endpoints)	Logistic regression for symptom improvement
HRQoL/Function improvement rate (EORTC QLQ-C30 endpoints)	Logistic regression for HRQoL/Function improvement
Time to HRQoL/Function deterioration (EORTC QLQ-C30 endpoints)	Stratified log-rank test and KM estimate plots
Time to symptom deterioration (EORTC QLQ-C30 and QLQ-LC13 endpoints)	Stratified log-rank test and KM estimate plots
Change from baseline in key symptoms (EORTC QLQ-C30 and QLQ-LC13)	Mixed model repeated measures analysis

BICR Blinded Independent Central Review; EORTC European Organisation for Research and Treatment of Cancer; HRQoL Health-related quality of life; ORR Objective response rate; PFS Progression-free survival; PFS2 Time from randomisation to second progression; QLQ-C30 v3 30-item Core Quality of Life Questionnaire, version 3; QLQ-LC13 13-item Lung Cancer Quality of Life Questionnaire; RECIST 1.1 Response Evaluation Criteria in Solid Tumours, version 1.1.

4.2.1 Primary efficacy endpoint – Progression-free survival

PFS based on the BICR data will be analysed using a stratified log-rank test adjusting for the stratification factors, i.e. level of PD-L1 expression ($PD-L1 < 1\%$ vs $PD-L1 \geq 1\%$) and prior therapy (cCRT or sCRT), for generation of the p-value. CIs for median progression-free survival will be derived based on Brookmeyer-Crowley method with a log-log transformation. The effect of durvalumab versus placebo treatment will be estimated by the HR together with its corresponding 95% CI and p-value. The HR and its CI will be estimated from a stratified Cox proportional hazards model (Cox, 1972) (with ties = Efron and the stratification variables included in the strata statement) and the CI calculated using a profile likelihood approach.

The stratification variables in the statistical modelling will be based on the values entered into Interactive voice response system (IVRS) at randomisation, even if it is subsequently discovered that these values were incorrect. Sensitivity analysis might be performed based on the values in the eCRF page if more than 10% randomised patients have discrepancies in stratification factors between IVRS and eCRF data.

These analyses, later named ‘main analysis’ below, will be repeated on the ITT set.

Supportive summaries/graphs

Kaplan-Meier plot of PFS will be presented by treatment arm, and repeated on the ITT set. Summaries of the number and percentage of patients experiencing a PFS event and the type of event (RECIST 1.1 or death) will be provided along with median PFS for each treatment and associated 95% CI, and repeated on the ITT set.

The assumption of proportionality will be assessed. Proportional hazards will be tested firstly by examining plots of complementary log-log (event times) vs log (time) and, if these raise concerns, by fitting a time-dependent covariate to assess the extent to which this represents random variation. If a lack of proportionality is evident, the variation in treatment effect can be described by presenting piecewise HR calculated over distinct time-periods. In such circumstances, the HR can still be meaningfully interpreted as an average HR over time unless there is extensive crossing of the survival curves. If lack of proportionality is found, this may be a result of treatment-by-covariate interactions, which will be investigated. In addition, the

KM curve along with landmark analyses (i.e. 6 months, 12 months, 18 months, 24 months, 36 months PFS rate) will be presented by treatment arm

The treatment status at progression of patients at the time of analysis will be summarised. This will include the number (%) of patients who were on-treatment at the time of progression, the number (%) of patients who discontinued study treatment prior to progression, the number (%) of patients who have not progressed and were on-treatment or discontinued treatment, and the number (%) of patients who progressed prior to receiving treatment. This will also provide distribution of number of days prior to progression for the patients who have discontinued treatment.

The number of patients prematurely censored will be summarised by treatment arm. A patient would be defined as prematurely censored if they had not progressed (or died in the absence of progression) and the latest scan prior to DCO was more than one scheduled tumour assessment interval plus 2 weeks (10 weeks if period between randomisation and DCO for that patient is 48 weeks or less; 14 weeks otherwise) prior to the DCO date.

Additionally, summary statistics will be given for the number of days from censoring to DCO for all censored patients.

A summary of the duration of follow-up will be summarised using median time from randomisation to date of censoring (date last known to have non-progression) in censored (not progressed) patients only, presented by treatment group.

Additionally, summary statistics for the number of weeks between the time of progression and the last RECIST 1.1 assessment prior to progression will be presented for each treatment group.

Summaries of the number and percentage of patients who miss two or more consecutive RECIST 1.1 assessments will be presented for each treatment group.

All collected RECIST 1.1 data will be listed. In addition, a summary of new lesions (i.e., sites of new lesions) will be produced.

Sensitivity Analyses

The following sensitivity analyses will be performed:

1. Evaluation-time bias

A sensitivity analysis will be performed to assess possible evaluation-time bias that may be introduced if scans are not performed at the CSP-scheduled time points. The midpoint between the time of progression and the previous RECIST 1.1 assessment (using the final date of the assessment) will be analysed using a stratified log-rank test, as described for the primary analysis of PFS. Note that midpoint values resulting in non-integer values should be rounded down. For patients whose death was treated as a PFS event, the date of death will be used to derive the PFS time used in the analysis. This approach has been shown to be robust to even highly asymmetric assessment schedules ([Sun and Chen 2010](#)). To support this analysis, the mean of patient-level average inter-assessment times will be tabulated for each treatment. This approach will use the BICR data. This analysis will be repeated on the ITT set.

2. Attrition bias

Attrition bias will be assessed by repeating the PFS main analysis except that the actual PFS event times, rather than the censored times, of patients who progressed or died in the absence of progression immediately following two, or more, missed tumour assessments will be included. In addition, and within the same sensitivity analysis, patients who take subsequent therapy prior to their last RECIST 1.1 assessment or progression or death will be censored at their last assessment prior to taking the subsequent therapy.

An attrition bias sensitivity analysis will also be performed. This analysis will be a repeat of the PFS primary analysis except that the actual PFS times of the patients who missed two or more tumour assessments (rather than censored times) will be used.

The above analyses will be supported by the Kaplan-Meier plot of the time to censoring using the PFS data from the primary analysis and where the censoring indicator of the PFS analysis is reversed. Except the supportive Kaplan-Meier plot, these analyses will be repeated on the ITT set.

3. Ascertainment bias

Ascertainment bias will be assessed by analysing site Investigator data. The programmatically derived PFS using the site Investigator date based upon RECIST 1.1 will be used. The stratified log-rank test, the HR and corresponding 95% CI will be provided as well as other pieces of the PFS main analysis. The number and percentage of patients experiencing a PFS event, and the type of event (RECIST 1.1 or death) along with median PFS for each treatment and associated 95% CI will also be produced. This analysis will be repeated on the ITT set.

If there is an important discrepancy between the primary analysis using the BICR and this sensitivity analysis using site Investigator data assessments, then the proportion of patients

with Investigator but no BICR progression will be summarised; such patients have the potential to introduce bias in the BICR due to informative censoring. An approach that imputes an event at the next visit in the BICR analysis may help inform the most likely HR value (Fleischer et al 2011), but only if an important discrepancy exists.

Disagreements between BICR and investigator reviews of RECIST 1.1 progression will be presented for each treatment group. The summary will include the early discrepancy rate which is the frequency of investigator declared progressions before the BICR review as a proportion of all investigator progressions, and the late discrepancy rate which is the frequency of investigator review declared progressions after the BICR as a proportion of all discrepancies.

A forest plot illustrating the HR and 95% CI will be provided to compare the primary and sensitivity analyses of progression-free survival. This analysis will be repeated on the ITT set.

4. Analysis by excluding sCRT patients with 1 concurrent chemotherapy and radiation cycle

Further sensitivity analysis will be carried out for PFS by excluding sCRT patients with 1 concurrent chemotherapy and radiation cycle using BICR tumour data based upon RECIST 1.1. The stratified log-rank test will be repeated on this data and HR and 95% CI will be presented. The following acceptance thresholds must be followed for patients to be accounted for in the excluded sCRT subpopulation:

- The window for sCRT patients receiving concurrent chemotherapy and radiation cycle is within 1 to 28 days prior to 1st dose of IP.
- Chemotherapy received must be platinum-based
- These patients must have received **at least** 3 cycles of chemotherapy (2 sequential and 1 concurrent) to be included in this excluded subgroup of patients, whereby
 - 2 sequential cycles: patients must have received at least 2 cycles of platinum-based chemotherapy before radiation therapy. The interval between administration of the last dose of the chemotherapy regimen and start of radiotherapy must be no more than 6 weeks.
 - 1 concurrent cycle: patients must have received at least 1 cycle of platinum-based chemoradiation therapy.
- The start date of last cycle of chemotherapy should be on or after the 7 days before start date of radiation therapy

5. The stratified Max-combo test will be conducted as a sensitivity analysis on the primary endpoint (PFS based on BICR data), to test for treatment differences in the case of nonproportional hazards. The analysis will be based on adaptive procedure involving selection of best test statistics with log-rank (G0,0) and the Fleming-Harrington (FH) test (G0, 1, G1, 0, and G1, 1) with alpha correction (Duke-Margolis, 2018).

6. Analysis accounting for COVID-19 deaths

This analysis is a repeat of the primary PFS analysis, but patients who have not progressed prior to death and where the primary or secondary cause of death is due to confirmed/suspected COVID-19 infection, or a confirmed/suspected COVID-19 infection is reported as a fatal AE, are censored at their last evaluable radiological assessment prior to their confirmed/suspected COVID-19 infection death date. This analysis will be performed if sufficient number of patients have such events (≥ 5 and/or $\geq 2\%$ of the patients in the analysis set).

Subgroup analysis / Additional analysis

Subgroup analyses will be conducted comparing PFS (per RECIST 1.1 using BICR assessments) between treatments in the following subgroups (but not limited to):

- Prior therapy (cCRT or sCRT)
- Stage of disease at study entry (IIIA vs. IIIB/C)
- Sex (Female vs. Male)
- Age at randomisation (< 65 vs. ≥ 65 years)
- Type of chemotherapy (cisplatin-based vs carboplatin-based)
- Time from last radiology to randomisation (< 14 days vs. ≥ 14 days)
- PD-L1 status (tumour cells [TCs] $\geq 25\%$ vs TCs $< 25\%$; TCs $\geq 1\%$ vs TCs $< 1\%$. Both sets are high vs. low/negative;)
 - PD-L1 status will be assigned based on the following algorithm:
 - Only sample with sample date on or before first dose should be used
 - Most recent sample “sampled date” should be used, unless this sample is unevaluable, in which case most recent evaluable sample is used
 - For multiple evaluable samples with the same sampled date, the sample with the highest PD-L1 % tumour membrane staining result should be used
- EGFR status (positive vs negative) - only applicable for analyses in the ITT set
- ALK status (positive vs negative) - only applicable for analyses in the ITT set
- EGRF or ALK status (positive vs negative) - only applicable for analyses in the ITT set

- Histology (squamous vs. non-squamous) WHO performance status at baseline (normal activity [PSTAT=0] vs restricted activity [PSTAT=1])
- Smoking (smoker vs. non-smoker [never smoked])
 - Patient is categorised as smoker if there exists a record in SU_NIC with any of the following options for “What type of substance was used?” 'Cigarettes', 'Cigarillos', 'Cigars', 'Pipe Tobacco', 'Tobacco for Smoking'. Else patient is a non-smoker. Non-smoker is a patient that has never smoked.
- Race (White, Black/African-American, Asian, Other [Native Hawaiian/Pacific Islander or American Indian/Alaska Native or Others])
- Race (Asian vs. non-Asian).

The subgroup analyses for the stratification factors will be based on the values entered into the IVRS, all other factors will be based on values recorded on the eCRF as indicated above.

Unless noted above, patients with unknown or missing level of baseline variables will be excluded from subgroup analyses.

Other baseline variables may also be assessed if there is clinical or biological justification or an imbalance is observed between the treatment arms. The purpose of the subgroup analyses is to assess the consistency of treatment effect across expected prognostic factors and/or predictive factors.

No adjustment to the significance level for testing of the subgroup and sensitivity analyses will be made since all these subgroup analyses will be considered exploratory and may only be supportive of the primary analysis of PFS. For each subgroup, the HR (for the treatment comparisons of interest) and 95% CI will be calculated from a Cox proportional hazards model that contains treatment. The Cox models will be fitted using SAS® PROC PHREG with the Efron method to control for ties, using the by statement to obtain HR and 95% CI for each subgroup level separately. These will be presented on a forest plot including the HR and 95% CI, along with the results of the overall primary analysis.

If there are too few events available for a meaningful analysis of a particular subgroup (it is not considered appropriate to present analyses where there are less than 20 events [10 events in each subgroup/treatment arm]), the relationship between that subgroup and PFS will not be formally analysed. In this case, only descriptive summaries will be provided.

Unless there is a marked difference between the results of the statistical analyses of the PFS from the BICR tumour data and that of the site Investigator, the subgroup analyses will only be performed upon the PFS endpoint using BICR data.

This analysis will be repeated on the ITT set.

Effect of covariates on the HR estimate

Cox proportional hazards modelling will be employed to assess the effect of pre-specified covariates on the HR estimate. The result from the model in the primary analysis and the model containing additional covariates will be presented.

Additional covariates for this model may include age at randomisation, sex, smoking status, stage of disease at study entry, best response to prior anti-cancer therapy (CR vs PR vs SD), histology, region and race.

The model will include the effect regardless of whether the inclusion of effect significantly improves the fit of the model provided there is enough data to make them meaningful.

Consistency of treatment effect between stratification factors

The presence of quantitative interactions will be assessed by means of an overall global interaction test for stratification factors.

This is performed by comparing the fit of a Cox proportional hazards model including treatment, all stratification variables, and all stratification variable-by treatment interaction terms, with a model that excludes the interaction terms and will be assessed at the 2-sided 10% significance level. Ties will be handled using the Efron approach.

If the global interaction test is found to be statistically significant, an attempt to determine the cause and type of interaction will be made. Stepwise backwards selection will be performed on the saturated model, whereby (using a 10% level throughout) the least significant interaction terms are removed one-by-one and any newly significant interactions re-included until a final model is reached where all included interactions are significant and all excluded interactions are non-significant. Throughout this process all main effects will be included in the model regardless of whether the corresponding interaction term is still present. This approach will identify the factors that independently alter the treatment effect and prevent identification of multiple correlated interactions.

Interactions between treatment and stratification factors will also be tested to rule out any qualitative interaction using the approach of Gail and Simon ([Gail and Simon 1985](#)).

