4.2.2 Secondary efficacy endpoints

4.2.2.1 Overall survival

The key secondary endpoint of OS will be analysed using a stratified log-rank test, using the same methodology as described for the primary PFS endpoint. The effect of durvalumab versus placebo will be estimated by the HR together with its corresponding (1 – alpha adjusted) % CI and p-value. Kaplan-Meier plot of OS will be presented by treatment arm.

The stratification variables in the statistical modelling will be based on the values entered into Interactive voice response system (IVRS) at randomisation, even if it is subsequently discovered that these values were incorrect. Sensitivity analysis might be performed based on the values in the eCRF page if more than 10% randomised patients have discrepancies in stratification factors between IVRS and eCRF data.

Summaries of the number and percentage of patients who have died, those still in survival follow-up, those lost to follow-up, and those who have withdrawn consent will be provided along with the median OS for each treatment.

This analysis will be repeated on the ITT set.

The assumption of proportionality will be assessed in the same way as for PFS.

Overall survival status will also be listed.

Sensitivity analyses

A sensitivity analysis for OS will examine the censoring patterns to rule out attrition bias, achieved by a Kaplan-Meier plot of time to censoring where the censoring indicator of OS is reversed.

Proportional hazards will be tested firstly by examining plots of complementary log-log (event times) vs log (time) and, if these raise concerns, by fitting a time-dependent covariate to assess the extent to which this represents random variation.

The stratified Max-combo test will be conducted as a sensitivity analysis on OS, to test for treatment differences in the case of non-proportional hazards. The same algorithm as specified in [section 4.2.1](#) for PFS will be used. This analysis will be repeated on the ITT set.

The number of patients prematurely censored will be summarised by treatment arm. A patient would be defined as prematurely censored if their survival status was not defined at the DCO.

In addition, duration of follow-up will be summarised using medians:

- In censored patients who are alive at DCO only: Time from randomisation to date of censoring (date last known to be alive) for each arm.

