- In all patients: Time from randomisation to the date of death or to the date of censoring for censored patients, regardless of treatment arm.

A sensitivity analysis will be performed to account for COVID-19 deaths. This analysis is a repeat of the primary OS analysis, but patients who died and the primary or secondary cause of death is due to confirmed/suspected COVID-19 infection, or a confirmed/suspected COVID-19 infection is reported as a fatal AE, are censored at their confirmed/suspected COVID-19 infection death date.

Subgroup analyses maybe performed if there is a sufficient number of OS events (≥ 20 events [≥ 10 events in each subgroup/treatment arm]). Subgroup analyses and a forest plot will be generated comparing OS between treatments in the same way as previously specified for PFS. This analysis will be repeated on the ITT set.

Cox proportional hazards modelling will be employed to assess the effect of pre-specified covariates on the HR estimate. The result from the model with and without additional covariates will be presented as specified for PFS.

Consistency of treatment effect between stratification factors will be analysed. Interactions between treatment and stratification factors will also be tested to rule out any qualitative interaction using the approach of Gail and Simon ([Gail and Simon 1985](#)), as previously specified for PFS.

4.2.2.2 **Proportion of patients alive at 12 months (OS12) and at 24 months (OS24)**

OS24 will be summarised (using the Kaplan-Meier curve) and presented by treatment arm along with 95% CI using the log-log transformation.

OS12 will be defined as the Kaplan-Meier estimate of OS at 12 months. The same analysis as for OS24 will be produced.

These analyses will be repeated on the ITT set.
Other landmarks may be summarised as appropriate.

4.2.2.3 **Objective response rate**

The ORR will be based on the programmatically derived RECIST 1.1 using the BICR tumour data, without the need for confirmation of the first documented response. The ORR will be

compared between durvalumab versus placebo using logistic regression models adjusting for the stratification factors as in the PFS analysis.

The results of the analysis will be presented in terms of an odds ratio (an odds ratio greater than 1 will favour the durvalumab arm) together with its associated profile likelihood 95% CI and p-value (based on twice the change in log-likelihood resulting from the addition of a treatment factor to the model). ^{CCI}

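### Follow-up for PFS is summarised in censored patients only, which understates it and makes it look shorter in the arm with more events; a reverse Kaplan-Meier median would largely correct this at almost no cost

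*SAP*

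**What the plan says.** **PFS.** Among the supportive summaries in SAP 4.2.1, duration of follow-up is the "median time from randomisation to date of censoring (date last known to have non-progression) in censored (not progressed) patients only", presented by treatment group.

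**OS.** SAP 4.2.2.1 gives two medians:
- For each arm: "In censored patients who are alive at DCO only: Time from randomisation to date of censoring".
- Pooled: "Time from randomisation to the date of death or to the date of censoring for censored patients, regardless of treatment arm".

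**Reverse Kaplan-Meier.** The SAP plans the curve that would describe follow-up better, but for another purpose and only as a plot. For PFS it sits under attrition bias, as a time-to-censoring plot "where the censoring indicator of the PFS analysis is reversed". For OS it is "a Kaplan-Meier plot of time to censoring where the censoring indicator of OS is reversed", again to examine attrition. Neither place asks for a median or ties the curve to duration of follow-up. The PFS plot is left out of the ITT repeat: "Except the supportive Kaplan-Meier plot, these analyses will be repeated on the ITT set".

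**The concern.** Median follow-up should say how long patients were, or could have been, observed. It should not depend on how they fared. The censored-only median breaks that rule: a patient enters it only by remaining event-free, and the longer ago a patient was randomised, the less likely that is. The median is pulled towards recent entrants, and pulled further in the arm with the higher event rate. The all-patients OS median breaks the rule differently, by counting an early death as short follow-up.

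What is at stake is how the results read. If durvalumab works, the by-arm PFS line will show longer follow-up on durvalumab than on placebo when there was no such difference. That invites a needless question about differential follow-up, and both arms will look less mature than they are. SAP 4.2.14 applies the same methods to the China cohort, so the figure would carry over there too.

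**Working it through.** The documents state no follow-up figure, so there is none to reproduce. The check asks what the SAP's definitions return when both arms have the same true follow-up.

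**Inputs from the documents**
- About 375 patients in the mITT set, randomised 2:1 (SAP 1.3), taken as 250 and 125.
- Scans every 8 weeks to week 48, then every 12 weeks, each ±1 week (SAP 3.1).
- Earlier study (protocol 2.3.1): placebo PFS median 5.6 months and PFS HR 0.52; OS medians 47.5 and 29.1 months and OS HR 0.68.

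**Assumptions, because the trial's own values are redacted**
- Uniform accrual over 22 to 36 months. Minimum follow-up 7 to 12 months for PFS and 7 to 43 for OS. The low values, 22 and 7, come from superseded text in the version history and serve only as one end of a range.
- Exponential times: placebo PFS median 5.6 to 8 months with HR 0.52 to 0.70, plus HR 1.0 as a check; placebo OS median 29.1 months with HR 0.68. Under HR 0.52 the durvalumab PFS median is 5.6/0.52 = 10.8 months.
- Censoring independent of the event.

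**Formula.** Let accrual last *a* months, minimum follow-up be *f*, and the hazard be λ. True follow-up is uniform on (*f*, *f*+*a*), with median *f* + *a*/2. Among patients still event-free, its density is proportional to exp(−λc), so the censored-only median is

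*f* − ln[½(1 + exp(−λ*a*))]/λ

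This is always below *f* + *a*/2 and falls as λ rises.

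**One case in full.** *a* = 22, *f* = 7; true median 7 + 11 = 18.0 months in both arms.
- Placebo: λ = 0.693/5.6 = 0.1238; exp(−22λ) = 0.0657; −ln(0.5328) = 0.6295; 7 + 0.6295/0.1238 = **12.1**.
- Durvalumab: λ = 0.693/10.77 = 0.0644; exp(−22λ) = 0.2427; −ln(0.6213) = 0.4759; 7 + 0.4759/0.0644 = **14.4**.

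Follow-up is understated by 3.6 and 5.9 months, with a gap of 2.3 months where none exists.

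**PFS by simulation at the planned size** (months; accrual + minimum follow-up)

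| Setting | True | Durvalumab | Placebo |
|---|---|---|---|
| 22+7, HR 0.52 | 18.0 | 14.4 | 12.1 |
| 22+9, placebo median 8, HR 0.65 | 20.0 | 16.8 | 15.5 |
| 36+12, HR 0.52 | 30.0 | 21.5 | 18.2 |
| 36+12, HR 0.52, 1%/month dropout | 24.9 | 15.8 | 10.2 |
| 36+12, placebo median 6, HR 1.0 | 30.0 | 18.2 | 18.6 |
| 22+7, HR 0.52, scan dates | 16.6 | 13.1 | 11.1 |
| 36+12, HR 0.52, scan dates | 28.5 | 20.0 | 16.6 |

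Without dropout or a scan grid, the formula gives 16.8/15.4 for the second row, 21.3/17.5 for the third and 17.9 in both arms for HR 1.0. The simulation runs a little higher where few patients are censored. In the third row that is about 5% of placebo, or 6 patients.

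The smallest shortfall is 20.0 − 16.8 = 3.2 months and the largest 24.9 − 10.2 = 14.7. With a treatment effect the gap runs from 16.8 − 15.5 = 1.3 to 15.8 − 10.2 = 5.6 months. At HR 1.0 the difference is simulation noise, but the shortfall is over 11 months.

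**OS, no loss to follow-up**

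| Setting | True | Alive at cut-off, durvalumab / placebo | All patients, pooled |
|---|---|---|---|
| 22+7 | 18.0 | 17.1 / 16.6 | 14.6 |
| 36+12 | 30.0 | 27.3 / 26.3 | 21.3 |
| 36+40 | 58.0 | 55.5 / 54.5 | 37.4 |

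**Reverse Kaplan-Meier median, same data.** With continuous times it was within about 0.8 months of the truth throughout: for PFS at 22+7, 18.0 and 18.2 against 18.0; for OS at 36+40, 58.0 and 58.2 against 58.0. With PFS scan dates at 22+7 it gave 17.2 and 18.0 against a true last-scan follow-up of 16.6.

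**The case against.** The strongest reply is that these are labelled descriptive conventions. Each median names its population, so nobody is misled about what was computed. Event counts, premature censoring by arm, days from censoring to cut-off and the reversed curves stand beside it. No inference uses it. All of that stands, and it is why the point ranks low. It does not make the figure a good measure of follow-up: a label does not tell the reader that the number moves with the treatment effect.

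Four stronger readings are tempting, and the documents or the calculations do not support them.

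- *The data cut-offs are affected.* The PFS and final OS cut-offs can be triggered by months of follow-up, but counted from the last randomisation (SAP 1.3 and 4.1.2). Median follow-up plays no part. Maturity in both documents is attached to event counts.
- *Every listed median can show a false arm difference.* The all-patients OS median is pooled across arms, so it can only be too short. The gap arises in the by-arm medians, mainly for PFS.
- *Reverse Kaplan-Meier gives the exact answer.* For PFS it does not. Under SAP 3.2.1 censoring falls on the last evaluable scan, is moved back before two missed visits, or is set at day 1. With ±1 week scan windows the reverse median was about 0.4 to 2 months high. It left an arm gap of about 0.4 to 1.0 month, with placebo the higher, and was imprecise in placebo (SD about 2 to 6 months). It is cleaner for OS.
- *The alive-at-cut-off OS median is always the lower figure.* With 0.6% per month lost at 36+40, it is 54.5/53.6 while reverse Kaplan-Meier gives 51.5/51.7, because it leaves out patients lost early. It is still below potential follow-up to the cut-off (58.0), but the two then answer different questions.

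**Conclusion.** The point holds as a reporting improvement. The by-arm PFS median in censored patients understates follow-up and makes it look shorter in the arm with more events. Given staggered entry and independent censoring, the direction follows from the definition. The size does not: about 3 to 15 months short, with a spurious gap of about 1 to 6 months, rests on assumed accrual, minimum follow-up, hazards and dropout.

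For OS the by-arm alive-at-cut-off median shares the bias in smaller form: about 1 to 4 months short, with a gap of 0.5 to 1 month, when no one is lost. The pooled all-patients median was 3.4 to 20.6 months short in the settings shown.

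Nothing in the testing, alpha, hazard ratios or cut-offs changes. The gain is a follow-up figure that depends much less on the outcome.

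**What to change.** In SAP 4.2.1 and 4.2.2.1, define duration of follow-up as the median, with 95% CI, of the Kaplan-Meier time to censoring with the event indicator reversed, by arm and overall. Take it from the curves already planned for attrition bias in those sections. Keep the existing medians as secondary lines with their populations named. For PFS, add a note that censoring falls on scan dates and the figure is approximate.

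The cost is one more line per table. The by-arm layout of the PFS reversed curve should be stated. Because that curve is not repeated on the ITT set, an ITT figure would need one further run if wanted. No new data, alpha or change to the primary analysis is involved.
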